9.4.5 Baseline Descriptive Statistics

[We will calculate descriptive statistics to allow adequate characterization of the sample. We will not use inferential statistics to compare the baseline groups.]

9.4.6 Planned Interim Analyses

[N/A]

9.4.7 Sub-Group Analyses

[N/A]

9.4.8 Tabulation of Individual Participant Data

[Individual participant data will be listed for pre and post measurements.]

[MagPro X100 Stimulator, Cool-B65 Butterfly Coil]

Page 32 of 39

9.4.9 Exploratory Analyses

[We hypothesize that following treatment those who received active HDS-TBS will have an increase in the anticorrelation of DLPFC-sgACC connectivity compared with pre-treatment and that the change in connectivity will be correlated with the change in depression severity. Analyses may be conducted on this. Additional analyses may be updated as needed in the future.]

10 SUPPORTING DOCUMENTATION AND OPERATIONAL CONSIDERATIONS

10.1 Regulatory, Ethical, and Study Oversight Considerations

10.1.1 Informed Consent Process

10.1.1.1 Consent/Assent and Other Informational Documents Provided To Participants

[Consent forms describing in detail the TMS administration, study procedures, and risks are given to the participant and written documentation of informed consent is required prior to enrolling in the study. Participants completing screening remotely will sign electronically in an IRB compliant system, such as REDCap. Consent materials are submitted with this protocol.]

10.1.1.2 Consent Procedures and Documentation

[Informed consent is a process that is initiated prior to the individual's agreeing to participate in the study and continues throughout the individual's study participation. Consent forms will be Institutional Review Board (IRB)-approved and the participant will be asked to read and review the document. The site will explain the research study to the participant and answer any questions that may arise. A verbal explanation will be provided in terms suited to the participant's comprehension of the purposes, procedures, and potential risks of the study and of their rights as research participants. Participants will have the opportunity to carefully review the written consent form and ask questions prior to signing. The participants can have the opportunity to discuss the study with their family or doctors or think about it prior to agreeing to participate if needed. The participant will sign the informed consent document prior to any procedures being done specifically for the study. Participants will be informed that participation is voluntary and that they may withdraw from the study at any time, without prejudice. A copy of the informed consent document will be given to the participants for their records. The informed consent process will be conducted and documented in the source document (including the date), and the form signed, before the participant undergoes any study-specific procedures. The rights and welfare of the participants will be protected by emphasizing to them that the quality of their medical care will not be adversely affected if they decline to participate in this study. Participants completing screening remotely will sign electronically in an IRB compliant system, such as REDCap.]

[MagPro X100 Stimulator, Cool-B65 Butterfly Coil]

Page 33 of 39

10.1.2 Study Discontinuation and Closure

[This study may be temporarily suspended or prematurely terminated by the Funding Sponsor or the PI at any site if there is sufficient reasonable cause. If the study is prematurely terminated or suspended, the Principal Investigator (PI) will promptly inform study participants, the Institutional Review Board (IRB), and funding sponsor and will provide the reason(s) for the termination or suspension. Study participants will be contacted, as applicable, and be informed of changes to study visit schedule.

Study may resume once concerns about safety, protocol compliance, and data quality are addressed, and satisfy the funding sponsor, IRB and/or Food and Drug Administration (FDA).]

In terminating the study, the Sponsor-Investigator will assure that adequate consideration is given to the protection of the subjects' interests.]

10.1.3 Confidentiality and Privacy

[Participant confidentiality and privacy is strictly held in trust by the participating investigators and their staff. Therefore, the study protocol, documentation, data, and all other information generated will be held in strict confidence. No information concerning the study or the data will be released to any unauthorized third party without necessary prior written approval.

All research activities will be conducted in as private a setting as possible.

The study monitor, other authorized representatives of the funding sponsor, representatives of the Institutional Review Board (IRB), regulatory agencies or pharmaceutical company supplying study product may inspect all documents and records required to be maintained by the investigator, including but not limited to, medical records (office, clinic, or hospital) and pharmacy records for the participants in this study. The clinical study site will permit access to such records.

The study participant's contact information will be securely stored at each clinical site for internal use during the study. At the end of the study, all records will continue to be kept in a secure location for as long a period as dictated by the reviewing IRB, Institutional policies, or other requirements.

Study participant research data, which is for purposes of statistical analysis and scientific reporting, will be transmitted to and stored to IRB compliant online databases, such as REDCap. PHI will be stored separately in secure cabinets inside locked rooms. Coded data will be stored on a secure server at the University of Pennsylvania through the Neuroscience Neuroimaging Group computing cluster. MRI data are securely copied on the uphs network directly from the MRI machine at Stellar Chance to this computing cluster without separate physical storage. Coded data are directly uploaded to the computing cluster from the computers on which the data are collected. The Penn computers are in a secured lab space and connected directly to the uphs encrypted network. The study data entry and study management systems used by clinical sites and by research staff will be secured and password protected.]

[MagPro X100 Stimulator, Cool-B65 Butterfly Coil]

Page 34 of 39

10.1.4 Future Use of Stored Specimens and Data

[Data collected for this study will be analyzed and stored to IRB compliant online databases, such as REDCap. De-identified data may be shared with approval from necessary committees with other investigators, with formal data-sharing agreement.]

10.1.5 Safety Oversight

[This is a low-risk study. Subject safety will be closely monitored. Subjects reporting side effects will be used to evaluate individual safety of iTBS. The PI will be monitoring the ongoing safety of subjects. PI is responsible for monitoring the data quality and the ongoing safety of subjects at respective site.]

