2.2 Background

[Li et al [3] first described the efficacy of a course of intermittent theta-burst stimulation (iTBS), a patterned form of repetitive transcranial magnetic stimulation (rTMS) over the left dorsal lateral prefrontal cortex (L-DLPFC) in patients with treatment refractory depression. In that study the degree of refractoriness was predictive of reduced efficacy, suggesting that highly refractory patients may require more TMS pulses to produce an antidepressant response. TBS has been shown to be more efficient than standard rTMS in modulating cortical excitability and multiple spaced iTBS (intermittent theta burst stimulation) sessions can be used to accelerate the treatment response. Recent work with transcranial magnetic stimulation (TMS) has shown that a rapid and sustained treatment response can be achieved by concentrating the usual 4-6 weeks of daily treatment into a high dose spaced theta burst TMS (HDS-TBS) treatment for 5 days [4]. Patients in that study were required to have failed conventional rTMS treatment and to meet deep brain stimulation inclusion criteria. However, that study only included MDD and excluded bipolar disorder. To date, there are no studies of HDS-TBS in bipolar disorder.

To demonstrate the feasibility of administering a high dose TBS protocol in our Center we recruited six patients with MDD into a pilot study using HDS-TBS according to the same parameters as will be used in the current proposal (10 treatments/day x 5 days), with the same stimulation settings. In our pilot study (IRB Protocol #834723), however, we only included participants with a diagnosis of MDD. Following treatment, patients had a mean reduction of 38.6% in depressive symptoms on the MADRS.]

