- **Pregnancy**: Although there are no known risks related to MRI on pregnant women or a fetus, there is a possibility of yet undiscovered pregnancy related risks. Since there is no possible benefit from participating in this protocol for a pregnant woman, we will exclude pregnant women.
- Incidental Findings Clause: This MRI is not a clinical scan. It is possible that during the course of the research study, the research staff may notice an unexpected finding(s). Should this occur, the finding(s) will be considered by the appropriate personnel and the PI will inform patients if necessary. These possible finding(s) may or may not be significant and may lead to anxiety about their condition and to further work-up by outside physician.

Worsening of Depression Symptoms. While participating in this study, symptoms worsen to the point where of needing psychological or medical support, patients will be given resources to emergency services. If a patient's symptoms require urgent attention, they will be informed to call 911 and present to the nearest emergency room or contact: Philadelphia Behavioral Health at [contact]. PBH hotlines are staffed 24 hours a day, 7 days per week. For similar hotlines outside of the Philadelphia area, they can consult www.suicide.org.

Risk to confidentiality. There is a rare risk that confidentiality could be breached in this study. Breaches in confidentiality could impact future insurability and/or employability.

[name] will provide clinical monitoring as needed. He will act as clinical and safety monitor and ensure compliance.]

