5.2 Exclusion Criteria

[An individual who meets any of the following criteria will be excluded from participation in this study:

- No current substance abuse disorder for the past 6 months (previous substance abuse not exclusionary)
- Any psychotic disorder or current active psychotic symptoms (personality disorders not exclusionary unless in the opinion of the referring psychiatrist it would jeopardize participation)
- No dementia or other major neurological disorders
- Not having depression as primary disorder
- No major medical illness, for example metastatic cancer, end stage renal disease
- Not able to verify contact information. Participants must be able to follow through with the study & must have verified contact information and at least one verified contact
- Pregnancy. While there are no known risks to a fetus this is a new use of TMS, which has not been tested, thus pregnancy is exclusionary
- Score on YMRS greater than 12 (patients with mixed features have been shown not to respond well to TMS treatment [10])
- Rapid cycling Bipolar illness (patients with > 4 mood episodes within the past year will be excluded, as they have a higher risk of switch to mania [11])

[MagPro X100 Stimulator, Cool-B65 Butterfly Coil]

Page 20 of 39

- Any implants, conditions, or contraindications that would be deemed unsafe for TMS or MRI
- Currently using benzodiazepines (such as lorazepam) with a dose >1 mg per day or equivalent]

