6.3 Measures to Minimize Bias: Randomization and Blinding

[Patients who are enrolled in the study (i.e., met inclusion/exclusion criteria) will be randomized to active TMS or Sham by a randomization system determined by the Independent Randomization Provider (IRP). This will occur at least one day before the start of treatment.

Only trained staff will administer the TMS treatment and the required clinical assessments during the study visits. These staff (as well as the PI and the patients) will also be blinded until the end of the study. Included in blinded status is the TMS operator since "active" vs "sham" delivery will be randomized and delivered in a blinded fashion. The only exception will be [name] (the study statistician) and [name] (clinical and medical monitor).]

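### Ongoing safety is assigned to a blinded PI, and no planned procedure compares accumulating harms by arm, although an unblinded medical monitor already exists

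*Combined protocol and SAP*

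**What the plan says.** Section 10.1.5 opens with "This is a low-risk study" and gives the oversight task to one person: "The PI will be monitoring the ongoing safety of subjects". It uses side-effect reports to judge the safety of individual subjects.

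Section 6.3 says of the staff who treat and assess: "These staff (as well as the PI and the patients) will also be blinded until the end of the study". Sections 4.1 and 6.3 exempt two people from blinding, the study statistician and the "clinical and medical monitor".

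The monitor's duties are spread over several sections. In 2.3.1 a person whose name is masked "will provide clinical monitoring as needed", and the text adds "He will act as clinical and safety monitor and ensure compliance". Section 6.4 gives the clinical and medical monitor intervention compliance. Section 10.1.6 has a named person work with the PI on site monitoring. None of these sets a review schedule, a cumulative listing, a split by arm or a reporting line.

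Section 8.3.5 has the PI evaluate each adverse event. Sections 9.4.4 (Safety Analyses) and 9.4.6 (Planned Interim Analyses) both read N/A. DSMB, DSMC and independent safety monitor appear only in the abbreviation list.

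**The concern.** Some harms can be recognised from a single case. A seizure during stimulation is one. Others cannot: a manic switch, rising suicidality or worsening depression in a patient with bipolar depression may simply be the illness. Whether active stimulation contributes shows only when events are counted by arm, and the person responsible for ongoing safety cannot see the arms.

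The protocol's own definitions also depend on frequency. Expectedness (8.3.4.3) and unanticipated problems (8.4.1) refer to the frequency of an event, and the unanticipated adverse device effect definition (8.3.3) to its degree of incidence. The blinded PI judges relatedness and expectedness, but nobody is assigned to track frequency in the active arm.

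Prior data for this population are thin. Section 2.2 states "To date, there are no studies of HDS-TBS in bipolar disorder", and the site's own pilot was six patients with MDD. Section 2.2.3 lists seizures, mania symptoms and suicidality, and section 5.2 excludes rapid cycling because of the risk of switch to mania. If active treatment did raise such risks, later participants would be treated without any planned look that could show it.

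**Working it through.** There is no figure in the plan to reproduce. The check is a comparison of sections, followed by an illustration of what a by-arm view adds.

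**Who sees what**
- PI: responsible for ongoing safety (10.1.5), blinded to the end (6.3), assesses events singly (8.3.5).
- Clinical and medical monitor: unblinded (4.1, 6.3). Written duties are compliance (6.4) and, if this is the same person as in 2.3.1, clinical and safety monitoring as needed.
- Statistician: unblinded (4.1, 6.3), with no safety task, because 9.4.4 and 9.4.6 are N/A.
- Data: YMRS and SSI are recorded on every treatment day, at Post Stimulation and at the 4-week visit (12.1). Section 4.1 describes the daily scales as tracking progress; 8.2 names only the MADRS for symptom monitoring during treatment.

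**Inputs for the illustration**
- 34 subjects (1.1). The allocation ratio is not stated; 1:1 is assumed, so 17 per arm.
- No event rates for the bipolar-specific harms are given; 10% to 30% in the active arm is assumed.

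**Pooled view against by-arm view.** If k patients are affected and risk is equal, the chance that all fall in the active arm is C(17,k)/C(34,k).
- k = 4: pooled 4/34 = 11.8%; by arm 4/17 = 23.5% against 0%; one-sided p = 2,380/46,376 = 0.051.
- k = 5: pooled 5/34 = 14.7%; by arm 5/17 = 29.4% against 0%; one-sided p = 6,188/278,256 = 0.022.

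**At a mid-trial look.** With 16 randomised there are about 8 per arm, and the chance is C(8,k)/C(16,k).
- k = 2: 28/120 = 0.23.
- k = 4: 70/1,820 = 0.038.

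**Chance of at least two events in the active arm**, 1 − (1−p)^n − n·p·(1−p)^(n−1):
- n = 4 (8 randomised): 5% at p = 0.10, 35% at p = 0.30.
- n = 8 (16 randomised): 19% at p = 0.10, 74% at p = 0.30.

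A look at 8 randomised would therefore usually have little to review. A look at about 16 has more, but a 2–0 split there is no signal. Only a marked split stands out from chance.

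**The case against.** The strongest reply is that an unblinded person with a safety title already exists. Section 2.3.1 names a clinical and safety monitor, 6.3 leaves the clinical and medical monitor unblinded, and nothing forbids that person from noticing an imbalance. A reader might infer from 10.1.5 that an active-arm harm cannot be seen during the trial. The documents do not support that. Ad hoc recognition is possible, and a single serious event can be acted on without unblinding (7.2, 8.3.5, 10.1.2). What stands is that no planned procedure would show an imbalance. That the roles in 2.3.1 and 6.3 belong to one person is itself inferred, because names are masked.

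Second, the risk label has a stated basis. Section 2.3.3 puts the risks no higher than in standard clinical TMS, and 2.3.1 says research on accelerated iTBS suggests no added side-effect risk. Enrolment requires a mood stabiliser and excludes YMRS above 12 and rapid cycling. A reader might set the words "this is a new use of TMS, which has not been tested" in 5.2 against the label, but they come from the pregnancy exclusion and explain only that criterion. The fair point is narrower: 10.1.5 does not address the absence of bipolar data stated in 2.2.

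Third, 9.4.1 plans plots of mean daily change in each score by arm. These might be read to include YMRS and SSI, but the efficacy data listed there do not name either scale, and means would blur a few individual switches. Adverse events would remain uncovered.

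Fourth, a trial this small has little power for harms, and a by-arm report could unblind. Both are true, and they shape the fix rather than remove the gap.

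**Conclusion.** The point holds as a gap in planned procedure. Ongoing safety sits with a blinded PI, events are judged individually, and no by-arm comparison of harms is planned during the trial or at its end. It would be too mild to say that the split merely waits for the final analysis, because 9.4.4 plans none.

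The size is modest. Under 1:1 allocation, four affected patients all in the active arm are 11.8% to the PI and 23.5% against 0% by arm, at one-sided p = 0.051. The review would reveal large imbalances only. A reader might infer that a mid-trial look would reliably protect the second half of the sample. The figures do not show that: the 10% to 30% event rates are assumed, and two events are not evidence of harm.

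Absence is judged on the public text, from which some pages were removed. This is a cheap improvement that should be made. It does not show that participants are unprotected.

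**What to change.** - **10.1.5:** assign the already unblinded clinical and medical monitor a scheduled review, by arm, of cumulative AEs, SAEs, YMRS and SSI at one or two fixed points, for example after about 16 randomised participants reach the Post Stimulation visit. Send the PI and IRB a written conclusion without arm data. Do not trigger a by-arm report by a single SAE, because that could reveal the participant's allocation to the PI, who rates relatedness.
- **9.4.4:** replace N/A with a descriptive table by arm of AEs, YMRS and SSI.
- **Reconcile** 10.1.5 with 2.2, 2.3.1, 6.3 and 6.4, so that one passage states who the safety monitor is, what is reviewed, when, and to whom a concern is reported.

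The cost is a wording amendment and a few hours of an existing role; the scales are already collected. The downside is a small risk that a report hints at the arms, which fixed timing and neutral wording limit. No stopping rule, efficacy look or new board is proposed.

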10.1.6 Clinical Monitoring

[Clinical site monitoring is conducted to ensure that the rights and well-being of trial participants are protected, that the reported trial data are accurate, complete, and verifiable, and that the conduct of the trial is in compliance with the currently approved protocol/amendment(s), with International Conference on Harmonisation Good Clinical Practice (ICH GCP), and with applicable regulatory requirement(s). [name] will work with the PI to ensure clinical monitoring is completed.]

10.1.7 Quality Assurance and Quality Control

[The site will perform internal quality management of study conduct, data collection, documentation and completion. All monitoring and audits are to be performed according to ICH GCP E6(R2). The investigational site will provide direct access to all trial related sites, source data/documents, and reports for the purpose of monitoring and auditing by the sponsor-investigator, and inspection by local and regulatory authorities.]

10.1.8 Data Handling and Record Keeping

10.1.8.1 Data Collection and Management Responsibilities

[Data collection is the responsibility of site under the supervision of the PI. The investigator is responsible for ensuring the accuracy, completeness, legibility, and timeliness of the data reported.

All source documents should be completed in a neat, legible manner to ensure accurate interpretation of data and follow ALCOAC standards (attributable, legible, contemporaneous, original, accurate, and complete).

Hardcopies of the study visit worksheets will be provided for use as source document worksheets for recording data for each participant enrolled in the study. Data recorded in the electronic case report form (eCRF) derived from source documents should be consistent with the data recorded on the source documents.]

[MagPro X100 Stimulator, Cool-B65 Butterfly Coil]

Page 35 of 39

10.1.8.2 Study Records Retention

[Study documents will be retained for the necessary time, as required by local regulations.]

10.1.9 Protocol Deviations

[The PI and the study team should document all scenarios where the protocol is not followed. They should assess whether the deviation is considered of significant impact (such as increasing risks to participants, etc.) and should be reported as required, with suggestions for corrective plans to prevent such occurrences.]

10.1.10 Publication and Data Sharing Policy

[This study will comply with the data sharing agreement. De-identified data may be shared with approval from the necessary committees with other investigators, with formal data-sharing agreements.]

10.1.11 Conflict of Interest Policy

[The independence of this study from any actual or perceived influence, such as by the pharmaceutical industry, is critical. Therefore, any actual conflict of interest of persons who have a role in the design, conduct, analysis, publication, or any aspect of this trial will be disclosed and managed. Furthermore, persons who have a perceived conflict of interest will be required to have such conflicts managed in a way that is appropriate to their participation in the design and conduct of this trial.]

